## **2.6 Blinding**

This is a double-blinded study. Neither the experimenter nor the subject will know whether they are giving or receiving caffeine. The code will be broken only after the study is complete. At this point all the research team will be made aware of the results as will the IRB. During the study the blind may be broken only in emergencies when knowledge of the subject's treatment group is necessary for further subject management. When possible, the Investigator will discuss the emergency with the monitor (the IRB) prior to unblinding.

## **2.7 Primary Study Endpoint**

The goal of the study is to determine whether caffeine speeds emergence from anesthesia. The primary endpoint will be a measurement made following termination of anesthesia in the human volunteers. This will be the time between terminating delivery of anesthetic and the subject opening his eyes. This measurement will constitute the "waking" time for each subject.

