**STUDY SUMMARY (DRUGS)**

TITLE	A Randomized, Double-Blinded, Placebo-Controlled Study to Determine if Caffeine Citrate (caffeine) Accelerates Emergence from Anesthesia
OBJECTIVES	To determine if caffeine will accelerate emergence from anesthesia.
PRIMARY OBJECTIVE	Determine whether subjects wake more rapidly from anesthesia after administration of caffeine as measured by the time between terminating anesthetic and the reinstatement of the gag reflex.
SECONDARY OBJECTIVES	Determine whether subjects wake more rapidly from anesthesia after administration of caffeine as measured by the time between terminating anesthetic and responding to simple commands (“squeeze my hand”).  Normally patients show cognitive impairments for hours after waking from anesthesia. We wish to determine whether caffeine administration ameliorates the cognitive impairment.
STUDY CENTER(S)	Single-center at University of Chicago
NUMBER OF SUBJECTS	Up to 8
DIAGNOSIS AND MAIN INCLUSION CRITERIA	Healthy male, ages 25-40 with no systematic diseases or conditions, metabolic equivalents of functional capacity, low risk for Obstructive Sleep Apnea, no history of arrhythmia, BMI < 30 kg/m  , no personal or family history of malignant hyperthermia, no history of any mental illness, no history of drugs or alcohol abuse, no history of seizure disorders or head trauma
DURATION OF SUBJECT PARTICIPATION AND DURATION OF STUDY	Subjects will be on study for up to 10 weeks
INVESTIGATIONAL PRODUCT	Caffeine Citrate
DOSE, ROUTE, REGIMEN	15 mg/kg body weight, given intravenously 10 min before the end of 1 hour isoflurane anesthesia

DURATION OF ADMINISTRATION	Study drug given intravenously across a 10 min time window
STATISTICAL METHODOLOGY	In this crossover study volunteers will serve as their own controls. The data will be analyzed with a paired t-test.

LIST OF ABBREVIATIONS

*EXAMPLES*

UCMC	UNIVERSITY OF CHICAGO MEDICAL CENTER
UC	UNIVERSITY OF CHICAGO
OCR	OFFICE OF CLINICAL RESEARCH
IRB	INSTITUTIONAL REVIEW BOARD
URA	UNIVERSITY RESEARCH ADMINISTRATION
ORS	OFFICE OF RESEARCH SERVICES
CRSO	CLINICAL RESEARCH SUPPORT OFFICE
UCCRC	UNIVERSITY OF CHICAGO CANCER CLINICAL RESEARCH CENTER
CRC	CLINICAL RESOURCE CENTER (FORMERLY GCRC)
DSMB	DATA SAFETY AND MONITORING BOARD

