## **2.8 Secondary Study Endpoints**

As a secondary endpoint for this study we will measure the time between terminating anesthetic and the subject being able to respond to a simple command ("squeeze my hand").

Normally patients receiving anesthesia exhibit significant cognitive problems for hours after anesthesia is terminated (references are provided below). Our goal is to determine whether caffeine helps ameliorate the cognitive issues. After waking, each subject will be asked to complete a series of psychomotor tests (described below), that will assess his reaction times, his memory and his motor control (ability to move his limbs). Details of the test are provided below.

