**6. STATISTICAL PLAN AND CONSIDERATIONS**

**6.1 Sample Size Determination**

Members of the IRB should understand that the sample size described above is an estimate, since we could not find good data on human “waking” times from isoflurane anesthesia in the literature. Thus we used our own animal studies to estimate sample size. There are at least three reasons why our sample size might be in error. First, rats are not people. They may get rid of isoflurane differently than do humans due to their higher respiration rates. In addition, rats are genetically more similar to each other than are humans. That would tend to increase human variance relative to that of the rat. On the other hand, the equipment used to anesthetize rats is less sophisticated than that in humans. In humans, the expired anesthetic concentration is measured, thereby allowing for precise anesthetic concentration, in the lungs. This is not possible in rats and so the anesthetic dose applied is less precise. This will tend to lower human variance. This is a long-winded way to say that our sample size estimate may be wrong. In these studies rats were used 4 times (twice with a saline injection twice with an injection of saline containing caffeine), a strategy that reduced variance.

Additional caveats: The 15 mg caffeine citrate that we propose is equivalent to 7.5 mg/kg of pure caffeine. We have never tested 7.5 mg/kg caffeine in rats, nor have we ever studied isoflurane at a concentration of 1 MAC.

We use the following stringent criteria to determine sample size: Power will be set to 95% and  $p \leq 0.01$ .

Rats waking from isoflurane anesthesia with 5 mg/kg caffeine (isoflurane ~ 1.5 MAC):  
(Control - saline injection) - Mean = 540 sec, SD = 159.04  
(Test - 5 mg/kg caffeine in saline injection) - Mean = 269.67 sec, SD = 103.69  
At this concentration of caffeine we would need  $n=12$  measurements for control and  $n=12$  measurements for caffeine to meet our stated stringent criteria. If each person were used for one control and one caffeine measurements we would need 12 people for the study.

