## 6.2 Statistical Methods

We hope to use a simple paired t-test to analyze the data, using volunteers as their own controls.

Crossover study - Each volunteer receives anesthesia 2 times: once without drug (control) and once with caffeine (test). Our animal studies suggest that variance is dramatically minimized when test subjects can be used as their own controls, in this manner. If humans recapitulate the rodent studies then 8 volunteers should provide an adequately

sized sample to answer the research question. The study was originally divided into two parts. The first part, the Pilot study has been completed.

Part 1: In order to demonstrate feasibility and safety, we carried out a pilot study of 2 healthy human volunteers to assess whether caffeine aids these subjects in recovering from isoflurane anesthesia. Recovery times were measured in three ways: as the time between the time when anesthetic is terminated until the subject starts to gag, can open his eyes, and the subject is able to respond to simple commands (like squeeze the clinician's hand). Each of the three endpoints was monitored and plotted separately. In this pilot study caffeine citrate (caffeine) was used at 10 mg/kg. By comparing subjects that wake from anesthesia who are injected with a saline solution to subjects that are injected with caffeine we were able to show that caffeine is as efficient in humans as in rodents. Now that we have demonstrated safety and feasibility, if the IRB gives us permission, we will continue to Part 2 of our study. Time from the end of anesthesia to eye opening will be analyzed, as will be the time from the end of anesthesia to response to a simple command. Each parameter (gagging, eye opening and response to command) will be analyzed and plotted separately.

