### **6.3 Subject Population(s) for Analysis**

The data from all subjects will be analyzed without knowledge of whether the data comes from a control or test condition. After breaking the code, data will be grouped accordingly. All data will be analyzed in two different ways. Using a paired t-test data from subjects that have completed the two anesthesia sessions of the study will be analyzed and plotted. Separately, using an unpaired t-test all data will be grouped together including that from subjects who did not finish the trial. In this way the data will be compared. Only data from subjects that failed the toxicology screen will be excluded.

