### 14. PUBLICATION PLAN

Data from the trial will be published as soon as the trial is complete regardless of whether the results confirm our working hypothesis. All subject identifiers will be removed as they are not required for publication. In addition to the primary endpoints (eye, opening and response to command) and secondary endpoints (psychomotor results), we will also publish vital sign information in the presence and absence of caffeine.

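### The primary endpoint is gag reflex in the summary, eye opening in 2.7, and eye opening plus response to command in section 14, and 6.2 ranks none of them

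*Combined protocol and SAP*

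**What the plan says.** The protocol ranks the emergence times in several places, and the rankings differ.

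- **Study summary, primary objective:** faster waking, "as measured by the time between terminating anesthetic and the reinstatement of the gag reflex". Response to command is listed under the secondary objectives. Eye opening is not mentioned.
- **Section 2.7:** a single primary endpoint. "This will be the time between terminating delivery of anesthetic and the subject opening his eyes". The gag reflex is not mentioned.
- **Section 2.8:** "As a secondary endpoint for this study we will measure the time between terminating anesthetic and the subject being able to respond" (the hand-squeeze instruction). The gag reflex is again absent.
- **Section 14:** "In addition to the primary endpoints (eye, opening and response to command) and secondary endpoints (psychomotor results"). Response to command is now primary, and only the psychomotor tests are secondary.
- **Section 6.2:** "Each parameter (gagging, eye opening and response to command) will be analyzed and plotted separately". No measure is marked as primary and no multiplicity rule is given.

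On the test, the summary states "The data will be analyzed with a paired t-test", and 6.2 names the same test in tentative terms. Section 6.3 keeps the paired test for volunteers who complete both sessions and then adds: "Separately, using an unpaired t-test all data will be grouped together including that from subjects who did not finish the trial". It does not say which of the two decides. The only significance level is p ≤ 0.01 in section 6.1, introduced by "We use the following stringent criteria to determine sample size". Neither 6.2 nor 6.3 gives an alpha or says whether the test is one- or two-sided.

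**The concern.** A confirmatory claim needs one result identified in advance as the one that answers the question. Here the current text supports three different answers, and no section is given precedence over the others. With 6 to 8 completers (section 2.2), the three times could easily fall on different sides of any threshold. Each of three headline results could then be presented as the planned one.

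The investigators have also already seen all three times in the two pilot volunteers (section 6.2), which makes an unambiguous advance choice more important. As written, a reader of the final report could not tell which p-value was confirmatory or what error rate it carries.

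**Working it through.** **1. Rank given to each measure, by section**

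| Section | Gag reflex | Eye opening | Response to command |
|---|---|---|---|
| Summary | primary | not mentioned | secondary |
| 2.7 and 2.8 | not mentioned | primary | secondary |
| 14 | not mentioned | primary | primary |
| 6.2 | analysed, no rank | analysed, no rank | analysed, no rank |

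No two of these rows agree. Section 5.2 does not settle it: it records gag reflex, eye opening, mouth opening, response to command and mask removal, with none marked as primary.

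**2. Does the sample size settle it?** Section 6.1 gives rat means of 540 s (SD 159.04) and 269.67 s (SD 103.69), 95% power and p ≤ 0.01, and states 12 per condition.

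- Difference: 540 − 269.67 = 270.33 s.
- Pooled SD: √[(159.04² + 103.69²)/2] = 134.25 s.
- Standardised difference: 270.33/134.25 = 2.01.
- Unpaired t-test (noncentral t), pooled SD: 11 per condition two-sided, 10 one-sided.
- Unpaired t-test, control SD for both conditions: 15 two-sided, 13 one-sided.

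The stated 12 is close to the two-sided pooled result (11), but it lies between these variants, so the intended sidedness cannot be recovered from it. The rat outcome was time until standing on four paws (section 1.1.3). That is none of the three human measures, so the calculation does not identify the primary endpoint either.

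**3. What the ambiguity could cost in type I error.** The plan states no rule that any of the three may count, so this is an illustration of that reading. The assumptions are no treatment effect, normal paired differences with a common correlation between endpoints, and two-sided paired t-tests. The plan gives no correlation, so 0.95 to 0 is covered. The 0.05 level is also an assumption.

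For k independent endpoints the chance of at least one false positive is 1 − (1 − α)^k:

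- k = 3: 1 − 0.99³ = 2.97%; 1 − 0.95³ = 14.26%.
- k = 2 (the section 14 pair): 1 − 0.99² = 1.99%; 1 − 0.95² = 9.75%.

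For positive correlation, 400,000 null trials were simulated per setting with 8 volunteers:

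| Correlation | Any of 3, α = 0.01 | Any of 3, α = 0.05 | Any of 2, α = 0.01 | Any of 2, α = 0.05 |
|---|---|---|---|---|
| 0.95 | 1.77% | 7.76% | 1.46% | 6.73% |
| 0.9 | 2.02% | 8.86% | 1.58% | 7.30% |
| 0.7 | 2.62% | 11.54% | 1.88% | 8.69% |
| 0.5 | 2.79% | 12.89% | 1.93% | 9.22% |
| 0 (exact) | 2.97% | 14.26% | 1.99% | 9.75% |

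With 6 completers and correlation 0.95, any of three gives 1.85% at 0.01 and 7.90% at 0.05; the figures at correlation 0 do not change with sample size. The choice between the paired and unpaired test is not modelled and would be a further source of flexibility.

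**The case against.** The strongest reply is that section 2.7 is the formal definition. Its heading is in the singular, it names eye opening, and it equates that time with waking. With 2.8, it already ranks eye opening above response to command. Section 14 is then a loose parenthesis in a publication plan, and the real conflict is only gag reflex against eye opening. The unpaired test in 6.3 reads naturally as a supplementary analysis that takes in dropouts, and p ≤ 0.01 can be read as the study's level. All three measures will be plotted and results published whatever they show, so a switch away from 2.7 would be visible. The inflation is hypothetical, and at 0.01 with high correlation it is under one percentage point.

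Much of this is fair on weight. Gag reflex against eye opening is the sharper conflict, the section 14, unpaired-test and alpha points are subordinate, and the figures at 0.05 rest on a level the plan does not contain. The publication commitment does make silent dropping of a measure less likely. But none of it resolves the contradiction. Nothing gives 2.7 precedence, 6.2 does not refer back to it, and the summary assigns the primary role to a measure that 2.7 and 2.8 omit. Publishing every measure does not tell a reader which one was confirmatory.

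**Conclusion.** The concern holds. The current text contains three incompatible statements of the primary endpoint, and the statistical section does not choose between them. This rests on the wording alone and needs no assumption. It bears on the trial's main conclusion, so it must be settled before the code is broken; a later correction could not restore prespecification.

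The numerical cost is secondary and conditional. If any of the three measures could be claimed, type I error at 0.01 rises to 1.8–3.0% with 8 volunteers, or 1.5–2.0% for the section 14 pair. If 0.05 were used it would be 7.8–14.3% and 6.7–9.8%. These ranges depend on the assumed correlations. The three times come from one emergence, so the low ends are the more plausible. With one named primary endpoint and one named test, the error rate returns to whatever level is stated.

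**What to change.** Before unblinding:

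1. Name one primary endpoint in identical words in the summary, 2.7, 6.2 and 14. Section 2.7 already supplies one, time from stopping the anesthetic to eye opening. If the investigators meant the gag reflex, 2.7 and 14 must change instead; the choice is theirs, but it must be made once.
2. List the other two times as secondary. If eye opening is primary, gag reflex has to be added to 2.8, which now omits it, and response to command removed from the primary list in 14. Either test them in a fixed order after the primary or report them as supportive; for a study of this size either is acceptable.
3. State in 6.2 and 6.3 that the paired t-test decides the primary result, and give its alpha and sidedness. If the p ≤ 0.01 of 6.1 is meant as the test level, say so. Label the unpaired all-data t-test as supportive.

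The cost is wording only, in the summary, 2.8, 6.2, 6.3 and 14. All three times are already recorded (section 5.2), so no extra data or volunteers are needed. The one downside is that a positive result on a secondary measure alone could not be claimed as confirmatory.

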## **2.8 Secondary Study Endpoints**

As a secondary endpoint for this study we will measure the time between terminating anesthetic and the subject being able to respond to a simple command ("squeeze my hand").

Normally patients receiving anesthesia exhibit significant cognitive problems for hours after anesthesia is terminated (references are provided below). Our goal is to determine whether caffeine helps ameliorate the cognitive issues. After waking, each subject will be asked to complete a series of psychomotor tests (described below), that will assess his reaction times, his memory and his motor control (ability to move his limbs). Details of the test are provided below.

## **2.9 Primary Safety Endpoints**

Throughout each anesthesia visit, the subject's vital signs will be monitored and there will be two experienced anesthesiologists present throughout the anesthesia session. Both anesthesiologists will be present for the first hour of the recovery time following the anesthesia. Once the test subject is awake, oriented with regards to time and space, and showing stable vital signs, typically about an hour after terminating the isoflurane, one of the anesthesiologists may leave the room. There will be one anesthesiologist present at all times until the subject is discharged.

At the conclusion of each "anesthesia" visit, we will discharge the subject based on the criteria used in our post anesthesia care unit in the hospitals. In general, the subject should be awake and alert with the stable vital signs. He should be able to drink clear liquid, void and ambulate before discharge home. We will call a car service for him without cost to the subject. The subject will be expected to live within 30 miles of The University of Chicago to make sessions easily accessible. Upon discharge from the

hospital, the subject will be required to be accompanied by a responsible adult. Each session for any given subject will be at least 2 weeks apart. The total time of each session, including the pre-anesthesia preparation, testing and recovery from anesthesia, will be ~4 hours. We will call the subject later the same day and then again the next day to make sure the subject fully recovers without any adverse event. The subject will get another call a week after the procedure. In some cases we may use emails or text messages rather than phone calls.

After the 2nd and final anesthesia session the subject will receive phone calls for the next two weeks to ensure complete recovery and no adverse effects.

### **3. SUBJECT SELECTION AND WITHDRAWAL**

#### **3.1 Number of Subjects**

For this study of up to 8 subjects will be tested. There will be a progress report to the IRB after 6 subjects.

#### **3.2 Gender, Age, Racial and Ethnic Origin of Subjects**

Healthy male, ages 25 – 40, all race and ethnic origin inclusive.

Our animal studies were carried out in adult male rats equivalent to the age range listed above. At present we would like to reproduce our animal studies in humans, introducing as few new variables as possible. The effects of anesthesia and the study drug on fetuses are not entirely known. The tests for early pregnancy are not 100% reliable. In males, pregnancy is not a possibility. Children can have adverse reactions to anesthetics, and they will not be recruited. Therefore, male volunteers are selected in this study. In order to further reduce the variables and minimize the risks for the subjects, exclusion criteria are used to select the subjects who are most suitable for this primary study.

#### **3.5 Inclusion Criteria**

1. Age 25-40
2. Male
3. Normal healthy subject without systematic diseases or conditions
4. Metabolic Equivalents of Functional Capacity  $\geq 5$
5. Low risk for Obstructive Sleep Apnea (OSA) based on the screening test (STOP-bang score established by American Society of Sleep Apnea): Yes to > 3 items- high risk of OSA
6. No History of Arrhythmia (Baseline EKG will be obtained during the history and physical session), seizure, liver and kidney diseases
7. BMI < 30 kg/m^2
8. No prior difficulty with anesthesia
9. No personal or family history of malignant hyperthermia
10. No history of any mental illness
11. No history of drugs or alcohol abuse (urine drug screens required).
12. Subjects capable of giving consent.
13. Living less than 30 miles away from UC.
14. No history of seizure disorders.

15. No history of head trauma.

### **3.6 Exclusion Criteria**

1. Age <25 or >40
2. Female
3. ASA physical status > 1 (normal healthy subject without systematic diseases or conditions)
4. Metabolic Equivalents of Functional Capacity (METs) < 5
5. High risks for Obstructive Sleep Apnea (OSA) based on the screening test (STOP-bang score established by American Society of Sleep Apnea): Yes to > 3 items- high risk of OSA
6. History Arrhythmia (Baseline EKG will be obtained during the history and physical session), seizure, liver and kidney diseases
7. BMI > 30 kg/m^2
8. Prior difficulty with anesthesia
9. Personal or family history of malignant hyperthermia
10. History of any mental illness
11. History of drugs or alcohol abuse (urine drug screens required)
12. Subjects capable of giving consent
13. Living more than 30 miles away.
14. History of seizure disorders.
15. History of head trauma.

### **3.7 Vulnerable Subjects**

No vulnerable subjects will be used.

### **3.8 Subject Identification & Recruitment**

Brochures, flyers and posters will be distributed throughout Chicago (at malls, stores, community clubs, minority centers etc).

Women will not be recruited to this study. The effects of anesthesia and the study drug on fetuses are not entirely known. The tests for early pregnancy are not 100% reliable. In males, pregnancy is not a possibility. Therefore, male volunteers are selected in this study. In order to further reduce the variables and minimize the risks for the subjects, exclusion criteria are used to select the subjects who are most suitable for this primary study.

Children can have adverse reactions to anesthetics and they will not be recruited.

Minorities will be actively recruited.

